## **Abstract**

*Background:* The impact of COVID-19 has been unequal across the nation in regards to number of cases, hospitalizations and deaths. Notably, primary strategies employed for COVID-19 mitigation at the national, state, and local levels (i.e. COVID-19 testing, vaccination rollouts, etc) often have inadequate reach in communities that experience COVID-19 disparities. Therefore, new approaches for COVID-19 mitigation are needed to more effectively reduce disparities. The current trial tests a novel approach by evaluating the efficacy of the Nurse-Community-Family Partnership (NCFP) intervention to improve primary (COVID-19 testing uptake) and secondary (COVID-19 vaccine uptake, adoption of COVID-19 infection control measures, household mutual aid capacity, and seasonal influenza vaccine uptake) outcomes in a community experiencing disproportionate COVID-19 morbidity, mortality, and barriers to mitigation.

*Methods:* In this two-arm parallel randomized control trial, we will evaluate the efficacy of the NCFP intervention in improving the primary and secondary outcomes. We will recruit 150 households from the Bronx in New York City. These households will be randomized in a 2:1 ratio, intervention:control, using a computer-generated algorithm. The NCFP intervention will take place over 5 months. The core components of the intervention include regular home visits by nurses and community health workers, development of a household-specific infection control plan, offer of at-home COVID-19 tests, and navigation to COVID-19 vaccination and other ancillary services. NCFP intervention components and intensity is informed by a household risk algorithm (low, medium, high). All households will complete a baseline assessment, monthly follow-up surveys during months 1-6 post baseline, and a delayed 9-month follow-up survey. We will use intent-to-treat analysis to evaluate the efficacy of the intervention in improving the primary and secondary outcomes compared to the standard of services. Subgroup analyses based on select household characteristics will be conducted.

*Discussion:* The NCFP intervention may have utility for mitigating COVID-19 at the household level—a novel and promising approach. If the trial achieves this, this care delivery model relying on a partnership between nurses, community health workers, and families will expand the available cadre of effective strategies for COVID-19 mitigation in underserved communities.

*Trial registration:* ClinicalTrials.gov NCT04832919. Registered on April 6th, 2021.

## **Keywords**

COVID-19, nurse-driven models of care, household intervention, testing, randomized control trial

## **Introduction**

### **Background and rationale {6a}**

Despite concerted efforts at the global, national, and local levels to mitigate the impact of COVID-19, the pandemic continues to inflict far-reaching health, socioeconomic, and political repercussions globally. In the US alone, the COVID-19 pandemic produced devastating health consequences with more than 80 million cases and 990,000 confirmed or probable deaths due to COVID-19 [1]. However, the impact of COVID-19 in the US has been unequal, with some communities experiencing substantially higher rates of COVID-19 cases, hospitalizations, and deaths. The disparities found in morbidity and mortality are driven by differences in exposure and susceptibility to COVID-19 across communities, with the greatest observed COVID-19 disparities occurring in communities where both elevated exposure and susceptibility exist [2]. Numerous community-level factors are associated with greater risk of exposure to COVID-19. For example, communities with large proportions of front-line workers who are in frequent face-to-face contact, heavily rely on public transportation, and live in crowded households located in densely populated areas are at a higher risk of exposure to COVID-19 [3]. Similarly, community-level factors can increase susceptibility to severe COVID-19 among those who are exposed. For example, communities that face poor access to timely health care, poor quality of care, and pre-existing health conditions are more biologically susceptible to COVID-19 morbidity and mortality [4-10]. In the US, residents in structurally underserved communities with elevated exposure and susceptibility to COVID-19 are disproportionately people of color and families with household incomes below the national average. As a result, there are pronounced disparities in COVID-19 cases, hospitalizations, and deaths along the lines of race/ethnicity and socioeconomic status are reflected in national data [4-10].

COVID-19 testing is one of the most important measures the global community has adopted to help mitigate the spread of the virus. Previous research demonstrates that testing was vital to slow the rate of transmission when undetected cases were widespread. Testing is also crucial in mitigating local spikes

and newly emerging waves of COVID-19. For example, a recent study showed college campuses across the US reduced the number of infection cases by 96% after imposing routine diagnostic tests of asymptomatic students [11]. Furthermore, early detection allows individuals to seek treatment before the illness progresses in severity and optimize their chances of survival. The importance of availability and uptake of testing for early detection of COVID-19 is particularly salient in the context of innovative antiviral medications (Sotrovimab, Nirmatrelvir-Ritonavir, Remdesivir, and Molnupiravir) that are currently available, and for which effectiveness appears higher early in the disease cycle [12]. According to Phase 2/3 results of the EPIC-HR study, the Nirmatrelvir-Ritonavir pill significantly decreased the risk of hospitalization or death by 89% for those who took the pill within the first few days of experiencing symptoms [12].

While the significance of COVID-19 testing is well-documented, existing barriers prevent communities who need it the most from receiving it. For instance, long wait-times, sparse testing locations, fear of contracting the virus at testing sites, and language barriers were among a few of the concerns voiced by these underserved communities [13]. Additionally, undocumented and/or uninsured individuals face more challenges when testing sites impose restrictions to receive free COVID-19 tests. This highlights the growing need for new approaches to expand testing availability for all, particularly in communities with elevated risk of exposure and susceptibility to COVID-19.

Throughout the COVID-19 pandemic, healthcare facilities helped increase testing rates by offering walk-in appointments, setting up drive-through sites, and sending out in-home testing kits [14]. While these strategies provide numerous options for individuals to get tested, it places the burden of seeking them out on the individual. Moreover, these options only accommodate those with their own means of transportation or those who can afford the high costs of at-home COVID-19 test kits. As a result, COVID-19 testing rates are disproportionately lower in underserved communities. Underserved communities that face structural barriers to COVID-19 testing tend to disproportionately make-up people of color. For instance, a study found that testing rates decreased as the percentage of ethnic-minority

residents residing in a New York City (NYC) neighborhood increased during the months of March and April of 2020 [15]. Existing evidence from health service delivery targeting other conditions suggests, nurse-driven approaches have utility for addressing these gaps. For example, an approach used regular in-home visits by nurses to successfully improve parental care and maternal life course in low-income families [16]. This method of by tailoring service delivery to the unique contexts of underserved communities presents an opportunity to improve reach of services and improve outcomes [16]. The implications of previous studies that use this strategy suggest similar nurse-driven approaches have the potential to address the challenges associated with COVID-19 testing.

The current randomized control trial (RCT) tests the efficacy of a new intervention that draws from previous nurse-driven approaches, the Nurse-Community-Family Partnership (NCFP) program. Similar to existing nurse-driven approaches, the program consists of regular in-home visits by nurses and community health workers. These nurses will employ a range of infection control measures, such as frequent in-home COVID-19 testing. They will also work with families to create and monitor the practice of an infection control plan uniquely tailored to the household's needs. Furthermore, community health workers will provide culturally appropriate support to the families, address stigma, medical mistrust, and help direct household members to a range of relevant services. This trial will be implemented in a sub-community in the US that pose at a greater risk to exposure and susceptibility of COVID-19: NYCHA households in Mott Haven, a neighborhood located in the Bronx, NYC. This intervention is designed to increase COVID-19 screenings and access to results as a way to improve these health outcomes. The overarching goal of this project is to inform current and future initiatives related to COVID-19 mitigation in similar socioeconomically underserved communities and households of color.

### **Objectives {7}**

The objectives of the study are to evaluate the efficacy of the Nurse-Community Health Worker-Family Partnership intervention to:

[figure not shown]
- a. Improve uptake of household COVID-19 testing

- b. Increase adoption of COVID-19 control measures as defined by:
  - i. Use of personal protective equipment (PPE)
  - ii. Frequent use of hand disinfectant and handwashing
  - iii. Maintenance of social distance
- c. Increase vaccine uptake
- d. Improve household-level mutual aid capacity as defined by family resiliency to secondary sequelae (psychological distress, financial insecurity, housing and food insecurity, job instability, substance abuse, and sexual behavior) and family cohesiveness.

## **Methods: Participants, interventions and outcomes**

### **Study setting {9}**

Since the start of the pandemic, the Bronx has had the highest rate of COVID-19 cases (140 per 1000), deaths (4.7 per 1000) and the lowest rate of COVID-19 testing per capita (35 per 1000) compared to other boroughs [1]. Many of the health and economic inequities that characterize the Bronx have made it difficult to combat these outcomes. Households will be recruited from public housing developments in Mott Haven, a neighborhood located in the South Bronx, New York City. Eleven buildings located in this neighborhood will be the catchment area for recruitment.

### **Eligibility criteria {10}**

#### Inclusion Criteria:

- Residence in one of the public housing complexes in Mott Haven, South Bronx
- English or Spanish-speaking
- Age 10 years or older
- Willing and able to provide informed consent or assent

#### Exclusion Criteria:

- Non-resident of one of the public housing complexes in Mott Haven, South Bronx
- Neither English nor Spanish speaker
- Younger than 10 years old
- Unwilling or unable to provide informed consent or assent

### **Who will take informed consent? {26a}**

A study staff member trained in human subjects protection will explain all study components, screen for eligibility, and obtain informed consent/assent from the participants. Participants who are 18 years or older will provide consent for themselves. Participants who are younger than 18 years will provide assent for themselves and their parent or legal guardian will provide consent for their child's participation as

well. All eligible participants must provide written consent/assent prior to enrollment and randomization to one of the study arms. During the consent process, the study staff member will emphasize the measures that will be taken to ensure confidentiality is not breached, including the use of encryption software to protect any identifiers.

#### Compensation:

Participants will receive a gift card after the completion of each survey (at baseline as well as monthly during months 1-6 and at 9 months post-baseline). This will total to an amount of \$270 United States Dollar (USD) in gift card value.

#### **Additional consent provisions for collection and use of participant data and biological specimens**

**{26b}**

Participants will be informed that all assessments and COVID-19 test results will be de-identified. Participant names will be replaced with a unique identification number, which only research staff have access to. Additionally, the consent forms explain how saliva/nasal swab samples may be collected for COVID-19 testing use from enrolled participants in the intervention arm. Only identified positive COVID-19 test results will be reported by name to the NYC Department of Health as part of the NYC COVID-19 test reporting protocol. This research is covered by a Certificate of Confidentiality from the National Institutes of Health (NIH); therefore, the research personnel will not disclose or use information that may reveal participants' names to any federal, state or local civil, criminal, administrative, legislative, or other action, suit, or proceeding, even if a court subpoena is issued. After the study is terminated, participants' data may be used for future research or stored in a data repository without obtaining additional consent.

#### **Interventions**

##### **Explanation for the choice of comparators {6b}**

This 2-arm randomized control trial will compare the efficacy of standard, publicly available COVID-19 testing and messaging to a Nurse-Community-Family Partnership intervention. The investigators

hypothesize that the NCFP intervention will improve household-level COVID-19 testing, COVID-19 vaccine and seasonal influenza vaccine uptake, adoption of COVID-19 infection control measures, and mutual aid capacity for households in the experimental group compared to the standard of care control group.

### **Intervention description {11a}**

#### *Experimental condition*

The NCFP intervention is delivered by nurses and community health workers (CHWs) as part of a collaborative partnership with households over the course of 5 months. On average, there will be three nurse-CHW home visits to households randomized to the intervention condition per month. Each visit will last for approximately 45 minutes on average.

The NCFP intervention prioritizes provision of intervention content based on three household risk levels: low, medium, and high. This intervention will use an algorithm to determine household-level risk to COVID-19. Low risk is defined by experience of no symptoms and no exposures by all household members. Medium risk is defined by experience of either symptoms (i.e. new cough, chest pain, fever above 100.4°, and/or loss of taste or smell) or an exposure to someone with known or suspected COVID-19 by any household member. High risk is established when a household member has a confirmed positive COVID-19 test. The algorithm will be informed by self-report of symptoms and exposures through a nurse hotline that is available for households placed in the intervention arm to use.

Additionally, nurses will conduct weekly phone screenings to continue monitoring household symptoms and exposures. For households that are at low risk, the intervention delivery team will provide the standard intervention content, which consists of (1) development and follow-up of an infection control plan tailored to the unique circumstances of the household, (2) printed NCFP family materials, (3) offer of monthly routine Polymerase Chain Reaction (PCR) COVID-19 test (self-administered saliva test), (4) provision of PPE (masks, hand sanitizer, gloves) and a thermometer, and (5) navigation to at-home or community-based COVID-19 vaccination services, as well as health, social welfare, vocational,

economic, or other support services as needed. For households that are at medium risk, in addition to the standard intervention content, the intervention delivery team will offer a rapid antigen COVID-19 tests to household members who are experiencing symptoms or were exposed and conduct enhanced symptom monitoring (daily phone screenings of new or worsening symptoms for seven days after report of symptoms or exposure). For households that are at high risk, nurses will additionally offer rapid antigen tests to all household members, enhanced symptom monitoring with all household members, and provide isolation support and guidance. In the event household members display any other acute emergency, nurses and CHWs will coordinate with the clinical triage team, where they will conduct triage, medical case management, monitoring, referrals to care, and follow-up.

In this intervention, nurses will supervise CHWs. Nurses will work with households on clinical and technical COVID-19 related issues, as well as build knowledge and skills that will help mitigate the spread and development of COVID-19 symptoms in households. For instance, nurses will offer routine in-home COVID-19 testing to all members of the household and deliver training on household infection control skills, including the safe and correct use of PPE, frequent use of hand disinfectant and handwashing, and social distancing techniques. The CHWs will serve as a culturally appropriate resource for families randomized to the intervention condition to ensure continued engagement and retention in the Nurse-Community-Family Partnership. CHWs will work with households to address expectancies, norms, and emotions that may represent barriers to COVID-19 testing and other related services. Additionally, CHWs will provide navigation to support services as needed.

#### *Treatment-as-usual condition*

Control participants will be informed of free COVID-19 testing, COVID-19 vaccination, and influenza vaccination sites located in the community and provided with the current NYC Department of Health standard COVID-19 information.

#### **Criteria for discontinuing or modifying allocated interventions {11b}**

No plans to discontinue interventions. Intervention messages may be modified in accordance with changing scientific evidence on COVID-19, COVID-19 mitigation, and Centers for Disease Control and Prevention (CDC) guidance.

### **Strategies to improve adherence to interventions {11c}**

There will be flexibility in scheduling NCFP visits (including on weekends), a reminder call to households before each scheduled visit to confirm, and reminders materials to highlight the importance of calling the nurse hotline in case of symptoms or exposure (e.g., a refrigerator magnet).

### **Relevant concomitant care permitted or prohibited during the trial {11d}**

There will be no restrictions imposed.

### **Provisions for post-trial care {30}**

At the end of the intervention phase, all households will receive information on available testing and vaccination sites in the community.

### **Outcomes {12}**

The primary outcome of interest is the following:

1. Household COVID-19 testing

Household COVID-19 testing uptake at the 9-month follow-up (9MFU) will be the primary outcome of interest. Our project will document testing uptake that is either administered by nurses or self-administered during home visits in the experimental arm, as well as self-reported information regarding COVID-19 testing uptake by study participants in the treatment and control groups. Participants will be asked whether they have received COVID-19 testing in the past three months, as well as about variables collected via the COVID-19 Symptoms, Diagnoses, and Testing scale. The COVID-19 Symptoms, Diagnoses, and Testing scale is adapted from the COVID-19 Cannabis Health Questionnaire. Specifically, participants will be asked questions regarding whether they are currently sick with an illness that might be related to COVID-19, any symptoms the participant experienced in the past three months, and the result of the participant's last COVID-19 test.

The secondary outcomes of interest are:

1. Household COVID-19 Testing Uptake

All medical services delivered by nurses during home-visits (such as COVID-19 test administration) will be carefully documented by the investigative team. At the time of the 6-month-follow-up (6MFU) assessment, the project team will obtain self-reported information regarding COVID-19 testing uptake by study participants in the treatment and control groups. Respondents will be asked whether they have received COVID-19 testing in the past six months. Respondents will also be asked questions from the COVID-19 Symptoms, Diagnoses, and Testing scale regarding whether they are currently sick with an illness that might be related to COVID-19, any symptoms the participant experienced in the past six months, and the result of the participant's last COVID-19 test.

2. COVID-19 control measure uptake

COVID-19 control measure uptake will be assessed using the COVID-19 Knowledge, Attitudes, and Avoidant Behaviors section of the Understanding America Study. Respondents will be asked questions on a 5-point Likert scale (Almost Never to Always), with higher values representing greater uptake of COVID-19 prevention behaviors (e.g., "Had close contact (within 6 feet) with people who do not live with you. "Gone out to a bar, club, or other place where people gather) and COVID-19 control uptake (e.g., "Worn a mask or other face covering." "Washed your hands with soap or used hand sanitizer several times per day"). COVID-19 control measure uptake will be assessed at the immediate follow-up (6 months) and at the delayed follow-up (9 months).

3. Vaccine Uptake

The investigators will obtain self-reported information and documentation of influenza and COVID vaccine uptake by study participants at the 6-month and 9-month follow-up assessments. Respondents will be asked if they received the flu shot [Yes/No] and whether they received the COVID-19 vaccine [Yes/No], the type of vaccine, and the number of doses.

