faced a disproportionate impact of COVID-19. Third, there is a possibility that cross-contamination may occur between the intervention and control groups. Meaning, there is a chance the control group may receive some portion of the intervention material without intending to. The research team has taken measures to prevent this from happening. The intervention delivery team (nurses and CHWs) will not be in contact with the control group at any point during the study. The research staff that do interact with the control group (i.e. through the recruitment process) will not have any knowledge of the intervention material; therefore, the language they use when recruiting or consenting the control group will not allude to what the intervention group will specifically receive. The intervention study arm will also be instructed to not share any intervention material with other families in their community. Furthermore, there is a possibility that not all eligible household members may be completely enrolled. For instance, there may be cases where a particular eligible age group within a household decides to not participate in the study. Nonetheless, this should be true in both study arms due to random assignment, so the chances of results being systematically skewed for one study arm and not the other arm would be low.

The NCFP intervention may offer an opportunity to improve COVID-19 mitigation strategies for underserved communities. The study is novel for integrating a care delivery team that is capable in assessing and meeting the needs of families who have been disproportionately impacted by COVID-19. We predict this program can be effective in improving COVID-19 testing uptake, COVID-19 vaccination uptake, COVID-19 infection control measures and seasonal influenza vaccine uptake in these communities. If the trial successfully achieves this, we infer this care delivery model has the potential to join national efforts in fighting COVID-19 by expanding the cadre of effective mitigation strategies designed for households.

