A Nurse-Community Health Worker-Family Partnership Model: Addressing Uptake of COVID-19 Testing and Control Measures

Statistical Analysis Plan (SAP)

Unique Protocol ID: 3P30DA011041-23S1

Protocol Version: 1.1

NCT #: NCT04832919

Document Date: 07/12/22

Contributors:

[name] – Senior Biostatistician

[name] – Junior Research Scientist/Data Manager

STATISTICAL DESIGN AND POWER

Measures.

Definition of Primary Outcomes

Household COVID testing uptake at the 9-month follow up is one of the main primary outcomes of interest. The investigative team will document all medical services administered by nurses during home visits, as well as self-reported information regarding COVID-19 testing uptake by study participants in the treatment and control groups. Participants will be asked whether they have received COVID-19 testing in the past three months [Yes/No]. Additionally, variables collected via the COVID-19 Symptoms, Diagnoses, and Testing Scale are the primary outcomes. This questionnaire is adapted from the COVID-19 Cannabis Health Questionnaire (CCHQ) (Vidot et al, 2020) and will measure COVID-19 symptoms, diagnoses, and testing. At the 9-month follow up point, participants will be asked questions regarding whether they are currently sick with an illness that might be related to COVID-19, any symptoms the participant experienced in the past three months [Check All That Apply], and the result of the participant's last COVID-19 test [Positive/Negative].

Definition of Secondary Outcomes

For the randomized trial, data collected utilizing the following questionnaires are secondary outcomes:

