COVID-19 control measure uptake, which is adapted from the COVID-19 Knowledge, Attitudes, and Avoidant Behaviors section of the Understanding America Study (CESR, 2020). Respondents will be asked questions regarding their engagement in behaviors associated with COVID-19 exposure on a 5-point scale [Almost Never, Sometimes, a Moderate Amount of the Time, Most of the Time, Always]. Greater values indicate higher frequency of uptake of COVID-19 prevention behaviors (e.g. "Canceled or postponed social activities." "Avoided riding the bus or subway") This questionnaire also includes questions regarding their uptake of COVID-19 control measures such as PPE usage and hand washing or sanitation. This will be measured both in immediate follow up (6 months), asking the participant to recall the past six months and also in delayed follow-up (9 months), asking the participant to recall the past three months.

Household COVID-19 Testing Uptake will be assessed as above, however at the immediate follow up time point (6 months). At the 6-month follow up point, participants will be asked whether they have received COVID-19 testing in the past six months [Yes/No]. Further, the COVID-19 Symptoms, Diagnoses, and Testing Scale will be administered at six months. Questions will ask respondents whether they are currently sick with an illness that might be related to COVID-19, any symptoms the participant experienced in the past six months [Check All That Apply], and the result of the participant's last COVID-19 test [Positive/Negative].

Vaccine Uptake will be documented by the study team via seasonal influenza and COVID-19 vaccination referrals by study nurses. Investigators will obtain self-reported information and documentation of influenza vaccine uptake by participants in both treatment arms by asking participants if they have received the influenza vaccine at the 6-month and 9-month follow up assessments [Yes/No] and whether they received the COVID-19 vaccine [Yes/No], the type of vaccine, and the number of doses.

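### Neither document says whether nurse test records and vaccination referrals, which exist in the intervention arm only, count towards uptake; the 6-month testing outcome and the SAP vaccine wording are the exposed parts

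*Protocol*

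**What the plan says.** **Testing at 9 months (primary).** Protocol, Outcomes {12}, names two sources. The first is "Our project will document testing uptake that is either administered by nurses or self-administered during home visits in the experimental arm". The second is "as well as self-reported information regarding COVID-19 testing uptake by study participants in the treatment and control groups". The survey item looks back three months. The SAP, Definition of Primary Outcomes, has the same pairing: "The investigative team will document all medical services administered by nurses during home visits, as well as self-reported information regarding COVID-19 testing uptake".

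**Testing at 6 months (secondary).** Protocol, Outcomes {12}: "All medical services delivered by nurses during home-visits (such as COVID-19 test administration) will be carefully documented by the investigative team". A self-report item with a six-month look-back follows. The SAP, Definition of Secondary Outcomes, says this outcome is assessed in the same way as the primary.

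**Vaccine uptake (secondary).** The SAP opens its definition with "Vaccine Uptake will be documented by the study team via seasonal influenza and COVID-19 vaccination referrals by study nurses". It then adds "Investigators will obtain self-reported information and documentation of influenza vaccine uptake by participants in both treatment arms", with yes/no receipt items for influenza and COVID-19 vaccine, vaccine type and number of doses. The protocol's own definition relies on self-report and documentation and does not mention referrals.

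**Control arm.** Protocol, Discussion: "The intervention delivery team (nurses and CHWs) will not be in contact with the control group at any point during the study". Protocol, Treatment-as-usual condition: "Control participants will be informed of free COVID-19 testing, COVID-19 vaccination, and influenza vaccination sites located in the community".

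Neither document states how the two sources are combined, which one decides that a participant counts as tested or vaccinated, or that the comparison between arms uses only the source common to both.

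**The concern.** Nurse records and referrals can exist in one arm only. If a nurse record is enough to count someone as tested, an intervention participant who forgets or fails to report a test is still counted, while a control participant who does the same is not. Sensitivity then differs by arm, the error favours the intervention, and a larger sample does not reduce it. The protocol's argument in its Discussion, that randomisation balances self-report bias, would no longer apply, because under-reporting would be corrected in one arm only.

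Referrals raise a second problem. A nurse test record documents a real test, but a referral is not a vaccination. Scoring it as uptake would add false positives in the intervention arm, equal to the share referred but not vaccinated.

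The open definition also leaves the choice of source to be made after the data have been seen.

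**Working it through.** **1. The plan's own figure.** Protocol, Sample size {14}, and SAP, Power and Sample Size: 100 and 50 households, 2 individuals per household, 3 timepoints, correlations 0.7 and 0.3 (the stated upper limits), proportions 0.10 and 0.10 + 0.15 = 0.25, alpha 0.05 (two-sided per SAP, Final Analysis).
- Design effect: 1 + (3 − 1) × 0.7 + 3 × (2 − 1) × 0.3 = 3.3.
- Effective observations: 600/3.3 = 181.8 and 300/3.3 = 90.9.
- Power: 86.4% (pooled variance) or 91.6% (unpooled). With 15% fewer households it is 79.8% or 86.8%.

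The stated power of more than 80% is reproduced and is not in dispute. The 15-point difference serves below only as a yardstick.

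**2. Do the visits fall inside each look-back window?** Protocol, Intervention description {11a}, gives 5 months of visits, taken here as about months 0–5.
- 6-month item: looks back six months, about months 0–6. It covers the whole visit period.
- 9-month item: looks back three months, about months 6–9. It begins 6 − 5 = 1 month after visits end, so visit records fall outside it unless a household's visits run more than about a month late.

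**3. Size if nurse records count.** The documents do not give these three quantities, so they are assumptions: true uptake p (set equal in both arms, to isolate ascertainment), self-report sensitivity s (equal in both arms, no false positive reports), and share r of intervention-arm testers who also have a nurse record (the same whether or not they self-report).
- Observed in intervention: p[s + (1 − s)r]. Observed in control: ps.
- Spurious difference: p(1 − s)r.

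| True uptake p | s = 0.95, r = 1 | s = 0.80, r = 1 | Range in points, r = 1 | Range in points, r = 0.5 |
|---|---|---|---|---|
| 0.10 (planned control rate) | 0.10 × 0.05 = 0.005 | 0.10 × 0.20 = 0.020 | 0.5–2.0 | 0.25–1.0 |
| 0.25 (planned intervention rate) | 0.25 × 0.05 = 0.0125 | 0.25 × 0.20 = 0.050 | 1.3–5.0 | 0.6–2.5 |
| 0.50 (illustrative) | 0.50 × 0.05 = 0.025 | 0.50 × 0.20 = 0.100 | 2.5–10 | 1.3–5.0 |

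To reach the full 15 points takes an extreme combination: p = 0.50, s = 0.70, r = 1, giving 0.50 × 0.30 = 0.15.

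**4. Effect on a nominal 5% test at 6 months.** For a single timepoint the design effect is 1 + (2 − 1) × 0.3 = 1.3, so the effective sizes are 200/1.3 = 153.8 and 100/1.3 = 76.9. With r = 1 and no true difference, the two-sided rejection probability for s = 0.95 to 0.80 is 5.0–7.0% at p = 0.10, 5.4–12.8% at p = 0.25 and 6.5–29.8% at p = 0.50.

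**5. Longitudinal model.** The SAP's Longitudinal Analysis is indexed by timepoint, so 6-month testing data can enter it. If an exposed 6-month difference were averaged with equal weight against an unexposed 9-month one, half of the step 3 figure would carry through.

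**The case against.** The strongest reply is that the endpoints are self-report and the nurse records are only delivery documentation. Protocol, Plans for assessment and collection of outcomes {18a}, describes self-reported surveys and keeps nurses and community health workers out of data collection. The limitations in the Discussion call the outcome measures self-reported. The SAP gives a single yes/no testing item. For vaccines, the protocol never mentions referrals, and the SAP also specifies receipt items. Much of this stands: nothing in either document says that a nurse record or a referral scores as uptake. A reader might infer that the plan has adopted an either-source rule, but the text does not support that. What remains is that the nurse sources sit inside the outcome definitions and nothing keeps them out of the comparison. The SAP's analysis for Aim 5 does use arm-specific sources for another outcome: in-home test results in the intervention group and self-reported results in controls.

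A reader might also infer that the 9-month primary comparison is materially biased. The windows in step 2 do not support this: if the endpoint is strictly the three-month item, r is about zero there.

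Finally, r = 1 is generous. Outside care is unrestricted, so some tests will be taken elsewhere and leave no nurse record. That objection is right, and it is why the table also shows r = 0.5 and the planned 10% rate.

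**Conclusion.** The concern holds as an unresolved definition, not as a demonstrated bias. If nurse records or referrals count, ascertainment is higher in the intervention arm. The exposure lies mainly in three places: the 6-month testing outcome, any longitudinal model that uses 6-month testing data, and the SAP's vaccine wording. For testing, the spurious difference would be 0.5–2.0 points at 10% true uptake, 1.3–5.0 at 25% and 2.5–10 at 50%, and half of that if half the testers have a nurse record. All of these rest on assumed values of p, s and r. The referral error cannot be sized, because the documents do not give the share referred but not vaccinated.

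It would go too far to conclude that the primary result is compromised: on the written schedule the direct effect on the three-month item is about zero. The point merits a clarification before analysis, but it is not among the defects that must be cured for the primary conclusion to stand.

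**What to change.** In Protocol, Outcomes {12}, and the SAP outcome definitions:
- State that 9-month testing, 6-month testing and vaccine uptake are scored in both arms from the same self-report items and look-back windows.
- State that vaccination documentation is requested in the same way in both arms, for both vaccines.
- Delete referrals as a source for vaccine uptake in the SAP.
- State that nurse test logs and referrals serve only to describe delivery and, for test logs, to check self-report accuracy within the intervention arm.

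This takes a few sentences and no new data, and should be dated before the outcome analysis. The price is that under-reporting stays uncorrected in both arms. With equal sensitivity a true 15-point difference would be observed as 15s: 0.80 × 15 = 12.0 to 0.95 × 15 = 14.3 points. Counting nurse records in one arm is not a neutral correction: with true uptake 0.25 and 0.10, s = 0.80 and r = 1, it would give 0.25 − 0.80 × 0.10 = 0.17, which overshoots the true 0.15. The change also does not remove any difference in reporting between arms that arises because participants know their allocation.
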